Title

Conservative versus Interventional Management of Postsurgical CSF
Pseudomeningocele: A Randomized Controlled Trial

NCT number

Not yet assigned

Unique protocol ID

108/20-55/2025

Date

22th May 2026

1. Background and Rationale

Background:

Postsurgical pseudomeningocele formation is a relatively common complication after intracranial surgery, often associated with fluid collection at the surgical site. Management approaches vary, with options including conservative treatment or interventional strategies such as revision surgery, insertion of lumbar drainage, or simple wound puncture. Current evidence on the most effective treatment is limited, and there is a need for randomized controlled trials to evaluate the outcomes of these approaches.

Rationale:

This trial aims to determine whether an interventional approach offers superior outcomes compared to conservative management in terms of pseudomeningocele absorption and overall patient recovery.

2. Objectives and Hypotheses

Primary Objective:

1. New onset of wound CSF leakage necessitating revision surgery

Secondary Objectives:

1. To compare the infection rate between the two treatment groups.
2. To assess functional recovery using the Glasgow Outcome Scale–Extended (GOSE) at 1 year post-surgery.
3. Absorption of pseudomeningocele at 4 months and 1 year post-surgery assessed by CT or MRI
4. Persistence of headache after the surgery – Pain Scale 0-10 (VAS)

Null Hypothesis:

There is no significant difference in the rate of CSF leakage and pseudomeningocele absorption at 4 months and 1 year, as measured by CT or MRI, between patients treated with conservative management and those undergoing interventional procedures (revision surgery, lumbar drainage, or simple puncture). Additionally, there is no significant difference in secondary outcomes, such as infection rates and functional recovery (measured by the Glasgow Outcome Scale–Extended), between the two groups.

3. Study Design

This study is a **parallel-group, randomized controlled trial** with two arms:

- **Interventional Group:** Patients undergoing local treatment - lumbar drainage insertion, simple wound puncture, fibrin glue or any combination.
- **Conservative Group:** Patients managed without surgical procedures, except for skin sutures.

Patients will be followed for a total of 1 year with CT or MRI assessments at 4 months and 1 year post-surgery.

4. Participants / Population

Inclusion Criteria:

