- Patients aged 18-80 years who have developed a pseudomeningocele following elective intracranial surgery.
- Diagnosed fluctuation during clinical examination after the surgery, Pseudomeningocele Palpation Scale (PPS), II-IV

I No or minimal fluctuation; underlying bone is clearly palpable with light palpation.

II Definite fluctuation; underlying bone or muscle is palpable with moderate pressure.

III Marked fluctuation; underlying structures are palpable only with firm pressure.

IV Tense lesion; painful and/or erythematous; underlying structures are not palpable even with firm pressure.

Light palpation: minimal pressure without causing discomfort

Moderate pressure: increased pressure causing awareness but no pain

Firm pressure: strong pressure causing discomfort or mild pain

- Willing and able to give informed consent.
- No prior history of previous cranial or spinal surgical intervention.

Exclusion Criteria:

- Patients with pseudomeningocele due to emergency or trauma-related surgeries.
- Known or suspected infection at the pseudomeningocele site at the time of recruitment.
- Severe comorbid conditions preventing participation (e.g., terminal illness, severe organ failure).
- Patients with conditions that require urgent surgical intervention not related to pseudomeningocele management.

5. Interventions

Interventional Arm:

- Patients will undergo one of the following procedures based on clinical judgment:
 1. **Revision surgery:** Surgical intervention to drain the pseudomeningocele and ensure proper wound closure.
 2. **Lumbar drainage insertion:** Placement of a lumbar drain to facilitate cerebrospinal fluid (CSF) diversion.
 3. **Simple puncture:** Needle aspiration of the pseudomeningocele under sterile conditions.

Conservative Arm:

- Patients will receive conservative management, with no surgical procedures other than the application of skin sutures if required. Monitoring and wound care will be provided.
-

6. Outcomes

Primary Outcome:

- **New onset of wound CSF leakage or tension pseudomeningocele necessitating revision surgery**

Secondary Outcomes:

- **Infection rate:**
Incidence of infection related to the pseudomeningocele or any interventions, including signs of local infection, meningitis, or systemic sepsis, within 1 year.
 - **Functional recovery (GOSE):**

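### The protocol contradicts itself on which procedures make up the interventional arm and on what counts as a primary event

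*Protocol*

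**What the plan says.** **The interventional arm.** The null hypothesis in Section 2 sets conservative management against "those undergoing interventional procedures (revision surgery, lumbar drainage, or simple puncture" (the bracket closes there). Section 3 describes the arm as "Patients undergoing local treatment - lumbar drainage insertion, simple wound puncture, fibrin glue or any combination". Section 5 states "Patients will undergo one of the following procedures based on clinical judgment" and lists three. The first is revision surgery: "Surgical intervention to drain the pseudomeningocele and ensure proper wound closure". The others are lumbar drainage and simple puncture; fibrin glue is not listed. Section 1 also names revision surgery among the interventional strategies. For the conservative arm, Section 5 allows "no surgical procedures other than the application of skin sutures if required".

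**The primary event.** The primary objective in Section 2 is "New onset of wound CSF leakage necessitating revision surgery". The null hypothesis in the same section speaks of the rate of CSF leakage and does not mention revision. Section 6 adds tension pseudomeningocele to the leak as a reason for revision. Section 9 compares the proportions requiring revision for a leak or tension pseudomeningocele, without saying that either must be new. Among the secondary outcomes, Section 6 also describes resolution or reduction of the pseudomeningocele as the primary outcome.

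**Entry.** Section 4 admits "Diagnosed fluctuation during clinical examination after the surgery, Pseudomeningocele Palpation Scale (PPS), II-IV", and defines the highest grade as "IV Tense lesion; painful and/or erythematous; underlying structures are not palpable even with firm pressure". No exclusion criterion mentions a wound leak at entry.

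**The concern.** A two-arm trial needs one description of the tested treatment and one definition of the event that decides it. Here a surgeon following Section 5 may reoperate as allocated treatment but has no provision for glue or combined procedures. A surgeon following Section 3 is in the opposite position. An outcome assessor, even if blinded, would classify the same patient differently depending on the section in hand. If the choice is left open in a trial where patients and surgical teams know the allocation, it may be settled after outcomes are known.

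A further worry is that revision surgery appears both as a possible allocated treatment and as the operation that marks a primary failure.

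**Working it through.** The plan gives no figure on this point. It states no primary event rate, no expected share of patients revised and no share of lesions tense at entry. The 30 per group in Section 8 is sized on absorption and serves here only as a denominator. The main check is a comparison of the texts.

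**1. The arm**

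| | Section 2 | Section 3 | Section 5 |
|---|---|---|---|
| Revision surgery | yes | no | yes |
| Lumbar drainage | yes | yes | yes |
| Puncture | yes | yes | yes |
| Fibrin glue | no | yes | no |
| Rule | list joined by 'or' | any combination | one procedure |

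The lists differ in content and in rule.

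**2. The event, tried on example patients**

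| Patient | Section 2 objective | Section 6 | Section 9, read literally |
|---|---|---|---|
| A. Enters at PPS II, new leak, revised for it | yes | yes | yes |
| B. Enters at PPS II, later tense without a leak, revised | no | yes | yes |
| C. New leak settled by skin suture, no revision | no | no | no |
| D. Interventional arm, PPS II–III without a leak, revised as allocated | no | no | no |
| E. Interventional arm, PPS IV at entry without a leak, revised as allocated | no | depends on parsing | can be |
| F. Conservative arm, PPS IV at entry without a leak, still tense, revised later | no | depends on parsing | yes |

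Patient B shows the contradiction without any assumption. Patient C counts only under the null hypothesis, which needs a leak and no revision. For E and F, Section 6 is unclear because its words on new onset may govern both the leak and the tension, or the leak alone.

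**3. When an allocated revision could be counted (patient E)**

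Three conditions are needed:
- Section 5's list governs rather than Section 3's.
- Section 9 is read apart from Section 6, or new onset in Section 6 governs leakage only.
- The lesion was tense or leaking at entry and was revised for that reason.

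This can happen in the interventional arm only, since the conservative arm has no allocated revision.

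**4. Illustration of size (all rates assumed)**

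Let f be the share of the interventional arm whose allocated revision is counted, p = 0.10 the true interventional rate and pc = 0.20 the true conservative rate. The true difference is 0.10 − 0.20 = −0.10. The counted interventional rate lies between max(f, p) and f + p, and is f + (1 − f)p if the two are independent.

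- f = 3/30: 0.10 to 0.20 (independent 0.10 + 0.90 × 0.10 = 0.19). Difference −0.10 to 0.00 (−0.01).
- f = 6/30: 0.20 to 0.30 (independent 0.20 + 0.80 × 0.10 = 0.28). Difference 0.00 to +0.10 (+0.08).
- The benefit vanishes at f = pc − p = 0.10 (3 of 30) if no patient is in both groups, and at f = pc = 0.20 (6 of 30) if every true event is among the counted revisions.

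If dropping new onset also adds a net 3 of 30 conservative events (patient F), the conservative rate becomes 0.30 and each difference moves by −0.10: −0.20 to −0.10 at f = 3/30, and −0.10 to 0.00 at f = 6/30. If Section 3's list governs, f = 0 and no allocated revision is counted.

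**The case against.** The strongest reply is that Section 9 is an analysis sentence, most naturally read as shorthand for the outcome in Section 6, and that counting rules such as the handling of lesions tense at entry are often left to a statistical analysis plan, which may exist. Section 9 also requires the revision to be for a leak or tension, so patient D is not caught. A procedure chosen by clinical judgment among three options is not plainly one that the patient required.

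Much of this stands against the double-counting point. A reader might infer that every allocated revision is scored as a failure, or that the trial is biased against intervention. The documents support neither. The overlap needs all the conditions in step 3, f cannot exceed the share of the arm tense or leaking at entry and revised for it, and the missing new-onset condition can add conservative events as well.

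The reply does not reach the two main contradictions. An analysis plan cannot decide which procedures surgeons perform, and Sections 2 and 6 differ on tension pseudomeningocele however Section 9 is read. Nor is Section 6 a clean safeguard, given its ambiguity over new onset.

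**Conclusion.** The protocol is wrong as written on two counts, and both must be corrected. The procedure lists and combination rules conflict, and the primary event is worded differently in Sections 2, 6 and 9, with the null hypothesis and the absorption paragraph adding to the conflict. These conclusions rest on the text alone, and confidence in them is high.

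The counting of allocated revisions as failures is a conditional consequence whose size is unknown. The figure of 3 to 6 patients of 30 depends on assumed rates of 20% and 10% and an unchanged conservative rate. It shows that a few patients could matter, not that a bias of that size or direction is expected. The need for correction does not depend on it.

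**What to change.** **Arm.** Use one procedure list and one rule, either one procedure or any combination, in Sections 2, 3 and 5. The clinical team should decide whether revision surgery stays. Removing it changes a treatment named in Sections 1, 2 and 5; keeping it contradicts the local-treatment description in Section 3. Either choice fixes the tested intervention and should be acknowledged as doing so.

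**Event.** Use one wording in Section 2 (objective and null hypothesis), Section 6 and Section 9, counted from randomisation in both arms: new wound CSF leakage, or new or recurrent tension pseudomeningocele not present at baseline, necessitating revision surgery. For lesions PPS IV at baseline, tension counts in either arm only if it recurs after having resolved. Revisions for tension that never resolved then fall outside the primary event and should be tabulated by arm, because persistence may differ between arms.

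**If revision surgery remains an allocated treatment.** Count the new leak, or the new or recurrent tension, itself, whatever operation treats it, and state that this changes the endpoint. Do not simply exempt the first allocated procedure: a new leak between randomisation and treatment must count in both arms.

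**Absorption.** Delete the words in Section 6 that label absorption the primary outcome.

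**Cost.** A protocol amendment with ethics review, since Section 10 says that the IRB has approved the protocol, and one case-report-form field for the indication for each revision. The primary event rate may be slightly lower under the tighter definition.

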The Glasgow Outcome Scale–Extended (GOSE) will be assessed at 1 year post-surgery to evaluate functional outcomes and quality of life. GOSE scores range from 1 (death) to 8 (upper good recovery).
 - **Pseudomeningocele absorption on CT or MRI:**
The primary outcome is the resolution or reduction of the pseudomeningocele, assessed through CT or MRI at **4 months** and **1 year** post-surgery. Scans will be reviewed by blinded radiologists, and pseudomeningocele size will be measured and recorded.
 - **Visual Analogue Scale**
-

7. Randomization and Blinding

Randomization:

Participants will be randomized in a 1:1 ratio to the interventional or conservative treatment arms using a computer-generated randomization sequence. Randomization will be stratified by age and body mass index.

Blinding:

Due to the nature of the interventions, patients and surgical teams cannot be blinded to group allocation. However, the radiologists interpreting the CT or MRIs and the independent data assessors evaluating outcomes will be blinded to the treatment arm.

8. Sample Size Calculation

A sample size of **60 patients** (30 per group) will be required to detect a clinically significant difference in pseudomeningocele absorption between the two groups, with a power of 80% and an alpha of 0.05.

9. Statistical Analysis

- **Primary outcome:**
The proportion of patients requiring revision surgery for CSF leakage or tension pseudomeningocele at 4 months and 1 year will be compared between the two groups using a chi-square test. Time-to-absorption analyses will be conducted using Kaplan-Meier survival curves and log-rank tests.
 - **Secondary outcomes:**
Infection rates will be compared using Fisher's exact test, and GOSE scores will be analyzed using a Mann-Whitney U test to assess differences in functional recovery between groups.
 - **Multivariate analysis:**
Multivariate logistic regression will be used to adjust for potential confounders, such as baseline health status, age, and type of initial surgery.
-

10. Ethical Considerations

The study will be conducted following the principles of the Declaration of Helsinki. Informed consent will be obtained from all participants before enrollment. The study protocol has been approved by the institutional review board (IRB). The risks associated with interventional approaches (e.g., infection, procedural complications) will be disclosed to patients during the consent process.

11. Follow-up and Monitoring

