Participants will be followed for a total of 1 year. Follow-up visits will include clinical assessments at **4 months** and **1 year**, as well as CT or MRI scans at these time points. Infection surveillance will occur throughout the study, and any adverse events will be recorded and reported to the IRB.

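### The infection outcome in Section 6 turns on a relatedness judgement that generally cannot be made without knowing the procedure, so blinded assessment is not secured and counting may differ by arm

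*Protocol*

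**What the plan says.** Section 2 lists as the first secondary objective: "To compare the infection rate between the two treatment groups". Section 6 makes this operational as "Incidence of infection related to the pseudomeningocele or any interventions, including signs of local infection, meningitis, or systemic sepsis, within 1 year".

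Section 7 describes who is blinded. On the treating side, "Due to the nature of the interventions, patients and surgical teams cannot be blinded to group allocation". On the assessment side, "the independent data assessors evaluating outcomes will be blinded to the treatment arm".

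Section 5 sets out the procedures. In the interventional arm, "Patients will undergo one of the following procedures based on clinical judgment", and the list is revision surgery, lumbar drainage and puncture. (Section 3 gives a somewhat different list; the point here does not depend on which applies.) The conservative arm has "no surgical procedures other than the application of skin sutures if required".

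Section 9 gives the test: "Infection rates will be compared using Fisher's exact test". Section 11 adds: "Infection surveillance will occur throughout the study, and any adverse events will be recorded and reported to the IRB". No section says who decides relatedness, or how procedure information is kept from the assessors.

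**The concern.** The outcome is not infection but infection that has passed a causal filter. The filter has two limbs: related to the pseudomeningocele, or related to an intervention. The second limb asks whether a drain, puncture or revision led to the infection, and that question is hard to answer without being told whether one was done. Either the assessor learns the procedure, and so in most cases the arm, or the attribution comes from the unblinded surgical team.

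The second limb is also unevenly spread. It is open to nearly everyone in the interventional arm and to few in the conservative arm. The same clinical event could therefore be counted in one arm and left out in the other.

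Infection is named in the null hypothesis, and Section 10 gives it as an example of the risks of the interventional approach. It is the main harm to set against any benefit, so a count that depends on the arm would distort the risk side of the comparison. The primary outcome is not touched.

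**Working it through.** The plan states no infection rate and no sample size for infection; the 60 patients (30 per group) in Section 8 are justified by absorption. So there is no figure of the plan's own to reproduce. The check is a reading of the text, followed by an illustration under assumptions.

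**1. How an infection comes to be counted**

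| Route | Interventional arm | Conservative arm |
|---|---|---|
| Related to the pseudomeningocele | Open to all (everyone has one, Section 4) | Open to all |
| Related to an intervention (procedures as in Section 5) | Open to all treated as assigned | Skin sutures, or revision surgery if a primary-outcome event occurs |

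All participants have also had elective intracranial surgery (Section 4). An assessor may put a meningitis down to that operation and not to the pseudomeningocele. In the conservative arm it would then usually drop out. In the interventional arm it could still come in through the second route. The term for interventions is not defined further; since Section 5 carries that heading and lists the trial procedures, those are its natural reading.

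**2. What the assessor must know**

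The diagnosis of a local infection or a meningitis needs clinical and laboratory findings, not the arm. Attribution to an intervention needs the procedure. Knowing the procedure is strong but not complete evidence of the arm, because sutures and revision surgery can occur in the conservative arm.

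**3. Illustration of size (all rates and fractions are assumptions)**

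Let both arms have the same true rate p, let every infection be counted in one arm and a fraction f in the other. Then the spurious difference is p × (1 − f), and the number of patients is 30 × p × (1 − f). The rejection probability is that of the two-sided Fisher test at 0.05 with 30 per arm, by exact enumeration.

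| True p | f | Counted rates | Spurious difference | Patients of 30 | P(reject), equal counting | P(reject), with f |
|---|---|---|---|---|---|---|
| 10% | 0.75 | 10% vs 7.5% | 2.5 points | 0.75 | 0.009 | 0.011 |
| 10% | 0.5 | 10% vs 5% | 5 points | 1.5 | 0.009 | 0.019 |
| 20% | 0.75 | 20% vs 15% | 5 points | 1.5 | 0.022 | 0.037 |
| 20% | 0.5 | 20% vs 10% | 10 points | 3 | 0.022 | 0.096 |
| 30% | 0.75 | 30% vs 22.5% | 7.5 points | 2.25 | 0.026 | 0.059 |
| 30% | 0.5 | 30% vs 15% | 15 points | 4.5 | 0.026 | 0.192 |

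With equal arm sizes the table reads the same whichever arm is undercounted; only the sign changes.

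**4. Set against what the test can detect**

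With 30 per arm, 0 versus 5 infections gives two-sided p = 0.052 and 0 versus 6 gives p = 0.024. At least six patients' difference is needed even when one arm has none. So in most of these scenarios the consequence is a biased estimate, and not a false significant result.

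**The case against.** The strongest reply is that the definition is a disjunction and its first limb covers every participant. A wound infection or meningitis in a conservative patient can be counted as related to the pseudomeningocele, and an assessor need not say which limb applied. This stands in large part. A reader might infer that blinded assessment of infection cannot work at all; the text does not support that. What remains is every case where the link to the pseudomeningocele is doubtful, such as sepsis with another possible source or a meningitis put down to the index operation. There the second limb decides, and it is uneven.

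A reader might also infer that the bias runs against the interventional arm. That does not follow. The wider definition pushes counts up there, but an unblinded team could equally be slow to attribute infections to its own procedures.

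Nor are unrelated infections lost for good. Section 11 plans surveillance throughout and recording of adverse events, so a count of all infections could be recovered. Nothing says, however, that those events would receive blinded assessment.

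Sections 2 and 6 should not be read as contradicting each other: the first names the objective and the second makes it operational. Finally, criteria for relatedness may sit in a document not shown, so their absence carries little weight. The point rests on the definition and the blinding statement, both of which the protocol itself fixes.

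**Conclusion.** The point holds in a limited form. The intervention limb of the infection outcome generally cannot be judged without procedure information, that information usually reveals the arm, and the limb applies mostly to one arm. This is in tension with the blinded assessment stated in Section 7 and leaves a secondary comparison open to differential counting.

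The size cannot be stated from the documents. Under the assumed rates of 10% to 30%, and with one half to three quarters of one arm's infections counted, the spurious difference is 2.5 to 15 points, or 0.75 to 4.5 patients of 30. The fractions are assumptions without a basis in the protocol, and half counted is strong for wound infection and meningitis given that the first limb covers everyone. A reader might take one to three patients to be as large as any effect this outcome could show; the Fisher results above rule that out. The damage is mainly to the estimate. The primary result is unaffected, and the trial is not sized for infection in any case. This is a worthwhile and cheap improvement and not a fatal flaw.

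**What to change.** In Section 6, drop the relatedness filter. Count every local infection (surgical wound, pseudomeningocele, or any drain or puncture site), meningitis or systemic sepsis with onset after randomisation and within 1 year, whatever its judged cause. The drain and puncture sites must be named, because the present wording captures them through its intervention limb and a list confined to wound infection could lose them.

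Add that the blinded assessors already planned in Section 7 classify these events with procedure details masked as far as possible, and that judged relatedness is reported only as a descriptive breakdown.

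The cost is a sentence or two of protocol text; surveillance and assessors are already planned, and the result matches the Section 2 objective directly. Two drawbacks remain. Sepsis unrelated to the wound will dilute the comparison slightly. And a drain-site or puncture-site infection may still unmask the arm, so the change reduces the problem without removing it entirely.

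### The protocol contradicts itself on the primary outcome and fixes no single primary time point, so the primary result could be chosen after the data are seen

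*Protocol*

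**What the plan says.** - **Section 2, primary objective:** "New onset of wound CSF leakage necessitating revision surgery". Tension pseudomeningocele is not mentioned and no time is given.
- **Section 2, secondary objective 3:** "Absorption of pseudomeningocele at 4 months and 1 year post-surgery assessed by CT or MRI".
- **Section 2, null hypothesis:** "There is no significant difference in the rate of CSF leakage and pseudomeningocele absorption at 4 months and 1 year". Leakage and absorption stand together here, before the sentence that turns to the secondary outcomes.
- **Section 6, primary outcome:** "New onset of wound CSF leakage or tension pseudomeningocele necessitating revision surgery". This is a wider event than in Section 2, again without a time.
- **Section 6, absorption item under the secondary outcomes:** "The primary outcome is the resolution or reduction of the pseudomeningocele, assessed through CT or MRI at" 4 months and 1 year.
- **Section 8:** 60 patients, 30 per group, are said to suffice to detect a difference in absorption "with a power of 80% and an alpha of 0.05".
- **Section 9, primary outcome:** "The proportion of patients requiring revision surgery for CSF leakage or tension pseudomeningocele at 4 months and 1 year will be compared" by a chi-square test. The same item continues: "Time-to-absorption analyses will be conducted using Kaplan-Meier survival curves and log-rank tests".

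**The concern.** A confirmatory trial needs one pre-specified answer to the question of which comparison decides it. Here a reader can defend three outcomes as primary: leak, leak or tension pseudomeningocele, and absorption. The revision comparison and the absorption assessment are each set at two times, with neither time designated.

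Leak needing revision and absorption on imaging are different events and need not favour the same arm, so the choice between them could change the trial's conclusion. Section 7 says that patients and surgical teams are not blinded, which makes advance commitment to one outcome more important. Two smaller consequences follow. The nominal 5% error rate is not secured if several comparisons may each be called primary. The power statement also belongs to an outcome that Section 2 lists as secondary.

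**Working it through.** **1. The sections side by side**

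| Place | Outcome treated as primary | Time |
|---|---|---|
| Section 2, primary objective | Leak needing revision | None |
| Section 2, null hypothesis | Leak and absorption jointly | 4 months and 1 year |
| Section 6, primary outcome | Leak or tension pseudomeningocele needing revision | None |
| Section 6, absorption item | Absorption on imaging | 4 months and 1 year |
| Section 8 | Absorption (basis of the sample size) | None |
| Section 9, primary outcome | Revision for leak or tension; also time to absorption | 4 months and 1 year; time to event |

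No two rows agree in full, and no sentence ranks the outcomes or the times.

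**2. The plan's own figure**

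The 60 patients cannot be reproduced, because Section 8 gives no rates, difference or standard deviation. Only the detectable effect can be recovered. Inputs: 30 per group, 80% power and alpha 0.05 (Section 8); two-sided testing is assumed. Solving

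n = [1.96·√(2p̄(1−p̄)) + 0.84·√(p₁(1−p₁) + p₂(1−p₂))]² / (p₁−p₂)²

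for n = 30 gives an absolute difference of about 31-36 percentage points for lower rates of 10-60% (33-39 points with continuity correction). For a continuous measure it gives a standardized difference of 0.72.

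**3. False-positive rate if any one of the three Section 9 tests counts**

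The tests are the chi-square at 4 months, the chi-square at 1 year and the log-rank test of absorption. Each is taken at 0.05. That is an assumption, because Section 9 assigns no alpha.

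- Ceiling: 3 × 0.05 = 15%.
- Independent tests: 1 − 0.95³ = 14.3%.
- Correlated normal tests: 13.0% if the two time points correlate at 0.7 and the log-rank is uncorrelated with them; 10.9% if all correlate at 0.7.
- Simulation with no effect, 30 per arm, revision and absorption independent. Assumed cumulative revision rates at 4 months/1 year were 10/15%, 15/20%, 20/22% and 20/30%; absorption rates were 50/75% and 40/70%.

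| Chi-square version | Two revision tests only | With the log-rank test |
|---|---|---|
| Uncorrected | 6.3-8.5% | 11.0-13.1% |
| Yates-corrected | 2.2-4.0% | 7.1-8.9% |

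The rounded range is 7-14%. Its upper end is the independent-test value and its lower end the corrected chi-square. With rarer revision (5% and 7%) and Yates correction, the three-test rate falls to about 5%.

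**4. Power if the revision composite is the primary outcome**

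With 30 per group, two-sided 0.05 and an uncorrected chi-square:

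power ≈ Φ{[|p₁−p₂| − 1.96·√(2p̄(1−p̄)/30)] / √[(p₁(1−p₁) + p₂(1−p₂))/30]}

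- 20% versus 10%: (0.100 − 0.181)/0.0913 = −0.88, so 19%.
- 30% versus 15%: (0.150 − 0.211)/0.106 = −0.58, so 28%.

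Exact enumeration gives 19% and 28%; with Yates correction it gives 10% and 19%. The rates are assumptions, since the protocol states none.

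**The case against.** The best defence is that the intent can be read. Revision-based leakage is primary in the Section 2 objective, under the Section 6 primary heading and in the opening sentence of the Section 9 primary analysis. Absorption is placed among the secondary items in Sections 2 and 6. On that reading the absorption sentence in Section 6 is a leftover. This is plausible, but it does not explain why Section 8 sizes the trial on absorption, why the null hypothesis joins the two, or why Section 9 puts time to absorption under the primary heading. Nor does it settle leak against leak or tension, or 4 months against 1 year.

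A second defence is that multiplicity rules are commonly left to a SAP, which is not shown here. That stands. A reader might infer that the trial has no alpha control and that every test is run at 0.05. The protocol does not say so: alpha appears once, in Section 8, for the sample size. A SAP could supply an error-control rule, but it cannot make these protocol sections agree.

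A reader might also put the false-positive rate as high as 17%, or treat 11% as a floor. Neither is supported. Values of 15-17% require separate absorption tests at 4 months and 1 year, which Section 9 does not list. Values of 11% and above require an uncorrected chi-square, whereas the protocol does not say which form is meant. If all results had to be significant, there would be no inflation.

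**Conclusion.** The contradiction over the primary outcome and the lack of one designated time are firm findings. They rest on the protocol's own text and on no simulation. They need correcting before the trial is registered, because as written the text allows the deciding comparison to be selected afterwards.

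The error-rate figure is conditional: roughly 7-14% instead of 5%, with a ceiling of 15%. It assumes that the three Section 9 tests are each run at 0.05 and that any single significant result counts as success. It varies with event rates, correlation and continuity correction, and approaches 5% when revision is rare and the chi-square is corrected.

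The 80% power statement applies to absorption only and does not carry over to the revision composite.

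**What to change.** 1. Name one primary outcome and one time point, identically in Sections 2, 6, 8 and 9, tested once at two-sided 0.05. State the origin from which the time is counted.
2. Make the other time point and the other outcome secondary. If absorption is not chosen, the time-to-absorption analysis moves with it.
3. Correct the sentence in the Section 6 absorption item that calls it primary, and limit the confirmatory null hypothesis to the chosen outcome.
4. Match Section 8 to the choice. If the revision composite is primary, restate the power of 30 per group for that composite with its assumed rates. If absorption is primary, state the rates or the difference behind the 60 patients.
5. If a revision-based outcome is kept, reconcile it with Section 5, which lists revision surgery among the interventional-arm procedures, so that the endpoint can be told apart from assigned treatment.

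**Cost:** the edits are cheap now, since the NCT number is not yet assigned. The outcomes not chosen become supportive. If the revision composite is chosen, the stated power may become much less favourable and the sample size may have to be reconsidered.
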